3 SUBJECT SELECTION

3.1 Accrual

This trial will enroll subjects with a diagnosis of relapsed or relapsed-refractory MM. Up to 18 DLT evaluable subjects will be enrolled in Phase I with 3 dose levels of ruxolitinib to be tested. Up to an additional 30 PFS4 evaluable subjects may be enrolled in the Phase II part at the MTD determined in Phase I.

All races and ethnic groups are eligible for this study.

3.1.1 Inclusion Criteria

Subjects must meet all the following criteria:

1. Documented history of relapsed and/or refractory multiple myeloma with > 2 lines of therapy. One of the prior lines of therapy must have been a carfilzomib containing regimen with evidence of relapse or progression within the last 60 days of the carfilzomib containing regimen with a carfilzomib dose of at least 27 mg/m². Carfilzomib containing regimen at the standard dose of 20/27 mg/m² is acceptable.
2. Measurable disease, as defined by at least one of the following:
 - a. Serum monoclonal protein level ≥ 0.5 g/dL for IgG, IgA, or IgM disease
 - b. Urinary M-protein excretion of ≥ 200 mg over a 24-hour period
 - c. Involved free light chain level ≥ 10 mg/dL, along with an abnormal free light chain ratio
3. Adequate bone marrow reserves, as defined by the following:
 - a. Absolute neutrophil count (ANC) ≥ 1000 cells/mm³ within 1 week of the initiation of treatment. G-CSF may not have been administered within 7 days of Cycle 1 Day.

- b. Platelet count of $\geq 75,000$ cells/mm³ for subjects who have bone marrow plasmacytosis of $< 50\%$, or $\geq 50,000$ cells/mm³ for subjects who have bone marrow plasmacytosis of $\geq 50\%$
4. Adequate hepatic function, as defined by the following:
 - a. Total bilirubin ≤ 2 times the upper limit of the institutional normal values
 - b. Total AST and ALT ≤ 3 times the upper limit of the institutional normal values
5. Adequate renal function, as defined by the following: creatinine clearance (CrCl) ≥ 30 mL/min., as measured by a 24-hour urine collection, or estimated by the Cockcroft and Gault formula.
6. Adequate cardiac function defined as LVEF $\geq 40\%$ by MUGA, echocardiogram or cardiac MRI.
7. Be 18-75 years of age
8. Eastern Cooperative Oncology Group (ECOG) performance status of 0–2.
9. FOCBP and male subjects who are sexually active with FOCBP must agree to use two highly effective (as determined per the Investigator) methods of contraception during the study and for 30 days (female subjects) or for 90 days (male subjects) following the last dose of study treatment including a male condom.
10. Written informed consent and HIPAA authorization for release of personal health information signed by the subject or his/her legally authorized representative.
11. Recovered from all reversible acute toxic effects of prior therapy (other than alopecia) to \leq Grade 1 or baseline.

3.1.2 Exclusion Criteria

Subjects must not meet any of the following criteria:

1. Non-secretory multiple myeloma
2. Known amyloidosis
3. Known POEMS syndrome (plasma cell dyscrasia with polyneuropathy, organomegaly, endocrinopathy, monoclonal protein, and skin changes)
4. Clinically significant illness including, but not limited to the following: active systemic infection, uncontrolled hypertension (as defined by BP $> 160/90$), New York Heart Association Class III and IV heart failure, unstable angina pectoris, myocardial infarction within the past 6 months of consent, uncontrolled cardiac arrhythmia, or any other condition (including laboratory abnormalities) that, in the opinion of the Investigator, places the subject at unacceptable risk for adverse outcome if he/she were to participate in the study
5. Prior cerebrovascular accident with persistent neurologic deficit.
6. Psychiatric illness/social situations that would limit compliance with study treatment and requirements

7. Pregnant or breast feeding. Females of childbearing potential (FOCBP) must have a negative serum pregnancy test within the 7 days prior to study drug administration and a negative urine pregnancy test within the 3 days prior to the first study drug administration.
8. Known human immunodeficiency virus (HIV) infection
9. Active hepatitis B and/or hepatitis C infection
 - Subjects with resolved HBV infection (i.e. subjects who are HBsAg negative but positive for antibodies to hepatitis B core antigen [anti-HBc] and/or antibodies to hepatitis B surface antigen [anti-HBs]) must be screened using real-time polymerase chain reaction (PCR) measurement of hepatitis B virus (HBV) DNA levels. Subjects who are PCR positive will be excluded. Exception: subjects with serologic findings suggestive of HBV vaccination (anti-HBs positivity as the only serologic marker) and a known history of prior HBV vaccination do not need to be tested for HBV DNA by PCR.
10. “Currently active” second malignancy, other than non-melanoma skin cancer and carcinoma in situ of the cervix, should not be enrolled. Subjects are not considered to have a “currently active” malignancy if they have completed therapy for a prior malignancy, are disease free from prior malignancies for >5 years and are considered by their physician to be at less than 30% risk of relapse. In addition, subjects with basal cell carcinoma of the skin, superficial carcinoma of the bladder, carcinoma of the prostate with a current PSA value of <0.5 ng/mL, or cervical intraepithelial neoplasia will be eligible. Finally, subjects who are on hormonal therapy for a history of either prostate cancer or breast cancer may enroll, provided that there has been no evidence of disease progression during the previous three years.
11. Known history of allergy to Captisol® (a cyclodextrin derivative used to solubilize carfilzomib).
12. Contraindication to any of the required concomitant drugs or supportive treatments or intolerance to hydration due to preexisting pulmonary or cardiac impairment including pleural effusion requiring thoracentesis or ascites requiring paracentesis.
13. Known intolerance to carfilzomib.
14. Co-administration with strong CYP3A4 inhibitors (such as, but not limited to, boceprevir, clarithromycin, indinavir, itraconazole, ketoconazole, lopinavir/ritonavir, ritonavir, mibefradil, nefazodone, nelfinavir, posaconazole, saquinavir, telaprevir, telithromycin, voriconazole) as well as fluconazole (a dual inhibitor of CYP3A4 and CYP2C9).

4 INVESTIGATIONAL PLAN

4.1 Milestone Date Definitions

Registration date: the date the subject signs the informed consent form.

Enrollment date: the date of initiation of study treatment on Cycle 1, Day 1. For the Phase I part of the study, this will be the date of initiation of treatment with carfilzomib, dexamethasone and ruxolitinib. For the Phase II part of the study, this is the date of initiation of treatment with carfilzomib and dexamethasone +/- ruxolitinib.

Treatment discontinuation date: the date the Investigator decides to discontinue the subject from study treatment.

4.2 Overall Study Design

This is an open label, Phase I/II protocol. This study will open as a multi-center study being conducted at Levine Cancer Institute (LCI) and additional investigational sites. Potentially, a total of 18 DLT evaluable subjects will be enrolled on the Phase I portion and up to 30 PFS4 evaluable subjects may be enrolled on the Phase II portion of this study. The study accrual period will be an estimated 36 months.

4.2.1 Phase I Design

Phase I will follow the standard 3 + 3 design with 3 to 6 subjects, depending on dose limiting toxicity (DLT) observed, at each dose level to be tested. Up to 3 dose levels will be tested. The overall duration of the Phase I portion of the study is expected to be no longer than 12 months.

Subjects will receive carfilzomib 56 mg/m²/day* IV over 30 minutes on Days 1, 2, 8, 9, 15 and 16 of a 28 day cycle. *Note: Subjects who have received CFZ < 56mg/m² more than 60 days prior to informed consent should receive CFZ 20mg/m² on Days 1 and 2 of the first cycle of protocol therapy with subsequent doses of 56mg/m².

Dexamethasone is administered orally prior to carfilzomib at 40 mg on Days 1, 8, and 15 of a 28 day cycle. Note: a 20 mg dose may be considered for subjects ≥ 75 years of age and for diabetic subjects.

Ruxolitinib is administered orally with or without food twice daily for 28 days of a 28 day cycle

Table 1: Dose Levels to be Tested

Cohort	Carfilzomib	Dexamethasone	Ruxolitinib
Each cycle is 28 days	IV over 30 min	PO	PO

	Days 1, 2, 8, 9, 15, 16	Days 1, 8 and 15	Twice Daily Days 1-28
Cohort 1	56 mg/m ^{2a}	40 mg PO ^b	5 mg
Cohort 2	56 mg/m ^{2a}	40 mg PO ^b	10 mg
Cohort 3	56 mg/m ^{2a}	40 mg PO ^b	15 mg

- a. Subjects who have received CFZ < 56mg/m² more than 60 days prior to informed consent should receive CFZ 20mg/m² on Days 1 and 2 of the first cycle with subsequent doses of 56mg/m². See section 4.2.1.1 for MTD guidance
- b. A 20 mg dose may be considered for subjects ≥ 75 years of age and for diabetic subjects.

4.2.1.1 Phase I Dose Escalation Guidelines

The first cohort of subjects enrolled in the Phase I portion of the study will receive dose level 1. A full safety evaluation will be conducted when these subjects have completed one cycle of combination therapy. Based on the evaluation after the first cycle, the dose escalation for subsequent subjects will proceed as follows:

- If no DLT is reported in the first three subjects at a dose level, that dose level will be considered safe, and three subjects will be enrolled at the next higher dose level.
- If 1 out of 3 subjects in a cohort at a dose level has a DLT, the dose level will be expanded to obtain six evaluable subjects. If 2 or more subjects in a cohort of 6 subjects at a dose level has a DLT, that dose level will not be considered safe, no further dose escalation will take place, and the MTD will have been exceeded*.
- If there is at most 1 subject with a DLT among an expanded cohort of six evaluable subjects, that dose level will be considered safe and a cohort of three subjects will be enrolled in the next higher dose level.

When the MTD has been exceeded:

If less than 6 subjects have been treated in the next lower dose level (the possible MTD level), additional subjects will be entered into this dose level until there are 6 subjects treated. If at most 1 of these 6 subjects encountered DLT, then this dose level will be declared to be the MTD. If 2 or more of the 6 subjects encounter DLT, then the MTD has been exceeded.

NOTE: If a subject discontinues treatment for reasons unrelated to adverse events such that safety in cycle one cannot be fully evaluated, an additional subject may be enrolled; this will be reviewed on a case by case basis.

4.2.1.2 Definition of Maximum Tolerated Dose

The MTD of the combination of carfilzomib, dexamethasone and ruxolitinib in multiple myeloma subjects shall be defined as the highest dose level resulting in at most 1 out of 6 subjects experiencing DLT in Cycle 1. The dose will be escalated in a new cohort until an MTD is identified or the maximum planned dose is achieved.

4.2.1.3 Definition of DLT

A dose-limiting toxicity (DLT) is defined as an adverse event or abnormal laboratory value assessed as related or possibly related to the study regimen that occurs within the first cycle of treatment and meets any of the criteria outlined below. National Cancer Institute CTCAE version 4.03 will be used for all adverse event grading.

- Grade 3 or greater non-hematologic toxicity possible/probable/definitely related to treatment. The following exceptions will apply:
 - Grade 3 nausea/vomiting or diarrhea for less than 72 hours with adequate antiemetic and other supportive care
 - Grade 3 fatigue for less than 1 week
 - Grade 3 or higher isolated electrolyte abnormalities that last up to 72 hours, are not clinically complicated, and resolve spontaneously or respond to conventional medical interventions
 - Grade 3 or higher amylase or lipase elevation that is not associated with symptoms or clinical manifestations of pancreatitis
 - Grade 3 tumor lysis syndrome (TLS) that lasts up to 72 hours, is not clinically complicated, and resolves spontaneously or responds to conventional medical interventions
- Grade 3-4 thrombocytopenia (platelet count < 50,000/ mm³) with clinically significant bleeding.
- Grade 4 neutropenia must occur for more than 5 days to be considered a DLT. A grade 4 neutropenia with duration of less than or equal to 5 days or grade 3 neutropenia must result in neutropenic fever with elevated temperature (defined as

ANC < 1000/mm³ with a single temperature of > 38.3°C or sustained temperature of ≥ 38°C for more than one hour) to be considered dose-limiting.

- Other grade 4 hematological toxicity (other than thrombocytopenia, neutropenia, leukocytopenia and lymphopenia)

The prophylactic use of G-CSF and platelet transfusions in cycle one of the dose escalation cohorts in Phase I is not permitted.

Once the MTD has been determined in Phase I, an additional 30 evaluable subjects will be enrolled and treated at the MTD. The evaluation of the MTD will be based on the toxicity observed during Cycle 1 of Phase I.

4.2.2 Phase II Design

Subjects in the Phase II/Run-in period will receive an initial cycle with carfilzomib at the twice weekly dose of 56mg/m² and dexamethasone. Following Cycle 1, a response assessment will be done. Subjects with a response of PR or better (“Responders”) will continue therapy with carfilzomib and dexamethasone. After these responding subjects subsequently progress, they will be treated with ruxolitinib (at the dose established in Phase 1) in combination with carfilzomib and dexamethasone. Subjects with a response of less than PR (“Non-responders”) will add ruxolitinib at the dose established in Phase I to carfilzomib and dexamethasone for all subsequent cycles. The cycle when ruxolitinib is added will be considered Cycle 1 (cycle numbers will start over). Disease evaluation assessment results should be available prior to dosing on Day 1 of each cycle of Phase II until initiation of ruxolitinib treatment (to ensure initiation of ruxolitinib occurs on Day 1 of a cycle).

Enrollment in the Phase II part of the study will be carried out in two stages. During the first stage, 10 PFS evaluable subjects (Section 13.3) will be enrolled. Enrollment and Stage 1 analysis of the first ten subjects on the three drugs (carfilzomib-ruxolitinib-dexamethasone) will be completed to determine if at least 3 of 10 subjects are alive and progression free at 4 months. If so, an additional 20 subjects will be enrolled (a total of 30 subjects) during the second stage. If at least 11 of 30 subjects are alive and progression free at 4 months, the null hypothesis will be rejected (based on binomial probabilities, see Section 13.1.2). The overall duration of the Phase II portion of the study is expected to be no longer than 24 months. For both Phase I and Phase II, subjects will be assessed for response after each cycle with confirmation of response according to IMWG response criteria regardless of dose level treated. Doses of each study drug may be interrupted or reduced in an attempt to manage toxicity.

Table 2: Phase II/Run-In Dosing^a

Drug	Dose	Route	Schedule	Cycle Length
------	------	-------	----------	--------------

Dexamethasone	40 mg ^b	PO	D1, 8, and 15 (Prior to carfilzomib)	28 days
Carfilzomib	56 mg/m ^{2c}	Intravenously (IV) over 30 minutes	D1, 2, 8, 9, 15, and 16	

^a All subjects enrolled in Phase II will initiate treatment in the Run-in Phase with the exception of subjects who previously received a carfilzomib regimen (prior to study enrollment) of ≥ 56 mg/m². These subjects will proceed directly to Phase II/Ruxolitinib (see Table 3). Subjects will have a disease response assessment prior to Cycle 2 (results must be available prior to Day 1 dosing) and will continue treatment in the Run-In until one of the following:

- Determined to be a “Non-responder” after Cycle 1 (defined as < PR per IMWG criteria) OR
- Determined to be a “Responder” after Cycle 1 (defined as \geq PR per IMWG criteria) with subsequent disease progression

After one of the above criteria are met, subjects will move into the Phase II/Ruxolitinib Phase (see Table 3)

^b A 20 mg dose may be considered for subjects ≥ 75 years of age or for diabetic subjects.

^c Subjects who previously received carfilzomib < 56mg/m² more than 60 days prior to informed consent should receive carfilzomib 20mg/m² on Days 1 and 2 of the first cycle with subsequent doses of 56mg/m²

Table 3: Phase II/Ruxolitinib Dosing^a

Drug	Dose	Route	Schedule	Cycle Length
Dexamethasone	40 mg ^b	PO	D1, 8, and 15 Prior to carfilzomib	28 days *note: Cycle numbers start over at Cycle 1 once ruxolitinib is initiated
Carfilzomib	56 mg/m ²	Intravenously (IV) over 30 minutes	D1, 2, 8, 9, 15, and 16	
Ruxolitinib	MTD from Phase I	PO	Twice daily from C1D1, continuously	

a. Subjects enrolled in Phase II will initiate ruxolitinib at one of the following time-points:

- Initiated treatment in the Run-In Phase and determined to be a “Non-responder” after Cycle 1
- Initiated treatment in the Run-In Phase, determined to be a “Responder” after Cycle 1 with subsequent disease progression
- Determined to have received carfilzomib regimen (prior to study enrollment) of ≥ 56 mg/m². These subjects will skip the Run-In Phase and proceed directly to ruxolitinib (in combination with carfilzomib and dexamethasone).

b. A 20 mg dose may be considered for subjects ≥ 75 years of age or for diabetic subjects

4.3 Subject Enrollment

Phase I

Enrolled subjects in Phase I will be DLT evaluable if they experience a DLT during Cycle 1 of treatment with the carfilzomib, ruxolitinib and dexamethasone regimen.

Enrolled subjects in Phase I who do **not** experience a DLT must meet all of the criteria below to be DLT evaluable:

- complete Cycle 1 of ruxolitinib therapy defined as followed
 - initiate Cycle 2, or
 - discontinue ruxolitinib therapy prior to Cycle 2 if the discontinuation date (as defined in Section 4.1) is on Cycle 1 Day 25 or later
- return no more than 20% of the number of ruxolitinib pills prescribed for Cycle 1 (while taking into account the actual length of Cycle 1)
- do not receive G-CSF or platelet transfusions during Cycle 1

Subjects who discontinue study treatment without experiencing a DLT and do not meet the DLT criteria as stated above will not be included in the 3+3 MTD evaluation but will be included in the overall analyses. Enrollment of new subjects to the current cohort will only be considered if there is less than the required number of DLT evaluable subjects to determine toxicity for the cohort. For example, of 3 subjects in a cohort, one withdraws due to disease progression, but 2 others have DLT, there is no need to continue enrollment to the given cohort as the MTD has already been exceeded. Alternatively, of 3 subjects in a cohort, one withdraws due to disease progression, but 2 others have not experienced a DLT, enrollment to the cohort will continue to fully evaluate the cohort with three DLT evaluable subjects).

Phase II

All enrolled subjects will remain in the intent to treat population. Enrollment to the Phase II part of the study will continue until the sample size requirements for the PFS4 evaluable population are achieved (Section 13.3).

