6 DOSE MODIFICATIONS

6.1 Phase I and Phase II Dose Modification and Dose Delay

Dose reductions are not permitted during Cycle 1 of Phase I unless the subject experiences a DLT. The subject may continue protocol therapy if the toxicity resolves, and the subject can be managed by a dose modification as detailed in this section. However, the occurrence of the DLT will be counted toward the assessment of the MTD. Dose reductions are permitted in subsequent cycles of Phase I and during all cycles of Phase II for clinically significant hematologic and non-hematologic toxicities. Held doses are not made up.

The prophylactic use of G-CSF and platelet transfusions in Cycle 1 of the dose escalation cohorts in Phase I is not permitted. Dose adjustments are permitted according to rules described in this section. Dose modifications different from those stated in the protocol should only be made in consultation with the Sponsor-Investigator; unless required for immediate subject safety.

Administration of the study drugs will be discontinued in the event of a treatment-related toxicity that persists despite appropriate dose reductions or any other toxicity that, in the opinion of the Investigator, warrants discontinuation.

Toxicity will be assessed using the CTCAE version 4.03 (Appendix [18.2](#)).

All dose modifications should be based on the worst preceding toxicity

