
Active HBV reactivation
	
 • Withhold carfilzomib until the infection is adequately controlled. If the benefits outweigh the risks, carfilzomib may be resumed with concomitant prophylaxis as per local standard of care. Consult a liver disease specialist as clinically indicated.

Active or suspected infection of any kind that requires systemic treatment
	
 • Hold carfilzomib until the infection has resolved and the course of antibiotics has been completed, if being treated with an anti-infective(s)

Other Grade 3 or 4 non-hematologic toxicity
	
 • Evaluate attribution and withhold the appropriate therapy. If resolved to \leq Grade 1 or baseline, restart the withheld therapy with one level dose reduction of suspected drug. • If tolerated, the reduced dose may be escalated to the previous dose at the discretion of the physician.

^a National Cancer Institute Common Terminology Criteria for Adverse Events (NCI CTCAE) Version 4.03

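### Phase I DLT evaluability sets no minimum carfilzomib exposure, so a subject who received few Cycle 1 infusions can count as having no DLT toward the three-drug MTD

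*Combined protocol and SAP*

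**What the plan says.** Under Section 4.3, a subject who has a DLT in Cycle 1 is evaluable. A subject without one "must meet all of the criteria below to be DLT evaluable". There are three criteria:

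- "complete Cycle 1 of ruxolitinib therapy defined as followed", which means starting Cycle 2 or stopping ruxolitinib on Day 25 or later;
- "return no more than 20% of the number of ruxolitinib pills prescribed for Cycle 1", allowing for the actual cycle length;
- "do not receive G-CSF or platelet transfusions during Cycle 1".

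Section 13.3 uses this list for dose escalation and the MTD, and adds only that Cycle 1 Day 1 treatment was started.

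Section 4.2.1.2 states: "The MTD of the combination of carfilzomib, dexamethasone and ruxolitinib in multiple myeloma subjects shall be defined as the highest dose level" with at most 1 DLT in 6 subjects. Table 1 defines each cohort with carfilzomib on Days 1, 2, 8, 9, 15 and 16.

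Section 6.1 bars Cycle 1 dose reductions in Phase I unless there is a DLT, but it does not bar holds, and "Held doses are not made up". For an infection that needs systemic treatment, the Section 6.3 table says "Hold carfilzomib until the infection has resolved and the course of antibiotics has been completed" and does not mention ruxolitinib.

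**The concern.** Only ruxolitinib is escalated, but the safety question is whether each ruxolitinib dose is tolerable on top of carfilzomib and dexamethasone. A subject without a DLT is informative about that only if the partner drugs were given. The sponsor already accepts the principle: the pill-return limit and the G-CSF and platelet exclusion exist so that a no-DLT result means something. Carfilzomib has no equivalent.

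The error can go in only one direction. A subject who has a DLT counts whatever the exposure, while a subject with little carfilzomib and no DLT counts as evidence of safety. Such a subject makes escalation more likely, and the dose declared goes forward to 30 Phase II subjects.

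**Working it through.** **The plan's own figure.** The Phase I maximum is 3 dose levels × 6 subjects = 18, as stated in Section 13.1.1. The point disputes no stated number, and a carfilzomib minimum leaves this maximum at 18 evaluable subjects.

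**Exposure limits as written.**
- Ruxolitinib: 20% of 28 days = 5.6 days. A 7-day hold is 7/28 = 25% of the pills, so if they are returned, a no-DLT subject is not evaluable.
- Carfilzomib: none.
- Dexamethasone: none.

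**A path that meets every criterion.** An unrelated infection is treated from Day 3 through Day 17.
1. It is not a DLT, because Section 4.2.1.3 requires at least a possible relation to treatment.
2. Section 6.3 holds carfilzomib, so the infusions of Days 8, 9, 15 and 16 are lost, even with the ±1 day window in the Table of Events. They are not made up.
3. The infection row leaves ruxolitinib alone, so the pill count is unaffected.
4. The non-hematologic criterion in Section 6.5 for starting a cycle concerns treatment-related toxicity, so it does not block Cycle 2.

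The subject is DLT-evaluable with 2 of 6 infusions.

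**Share of planned Cycle 1 carfilzomib received.** The doses come from Section 4.2.1. The plan is 6 × 56 = 336 mg/m², or 2 × 20 + 4 × 56 = 264 mg/m² for a subject given the 20 mg/m² start.

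| Infusions received | 56 mg/m² from Day 1 | 20 mg/m² on Days 1-2 |
|---|---|---|
| Days 1 and 2 only | 112/336 = 33% | 40/264 = 15% |
| One 56 mg/m² week lost | 224/336 = 67% | 152/264 = 58% |

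In the 15% case the subject never received 56 mg/m², yet counts toward a cohort defined at that dose.

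**Effect on escalation (illustration).** The documents give no DLT rates, so these are assumed. Under Section 4.2.1.1, P(escalate) = P(0 DLT in first 3) + P(1 in first 3) × P(0 in next 3).

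At a true rate of 33% with everyone fully exposed: 0.67³ + 3(0.33)(0.67²)(0.67³) = 0.301 + 0.134 = 0.434. If one of the first three subjects is under-exposed and has no DLT risk: 0.67² + 2(0.33)(0.67)(0.67³) = 0.449 + 0.133 = 0.582.

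| Assumed true DLT rate | All fully exposed | One of first three under-exposed (that subject's risk: half the true rate, down to 0) |
|---|---|---|
| 20% | 0.709 | 0.756 to 0.804 |
| 33% | 0.434 | 0.508 to 0.582 |
| 50% | 0.172 | 0.242 to 0.312 |

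**The case against.** **The routes are narrow.** This largely stands. Neutropenia, Grade 4 or bleeding thrombocytopenia, hepatic and renal holds stop both drugs, and a ruxolitinib stop beyond 5.6 days would usually fail the pill criterion. A related Grade 3 or higher non-hematologic event behind a carfilzomib hold would normally itself be a DLT. A reader might infer that every hold row naming only carfilzomib leaves the subject on ruxolitinib. The documents do not support that: for suspected PML, Section 5.3.1 stops ruxolitinib, although the Section 6.3 row does not say so. The infection hold is also described in two ways. Section 5.1.3 ties it to infection needing IV systemic treatment, Section 6.3 to systemic treatment of any kind. Under the narrower description the route shrinks but stays open. Missed infusion visits are a further route.

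**There are other safeguards.** Section 4.2.1.1 places the safety evaluation after one cycle of combination therapy. Its replacement note covers subjects who discontinue for reasons other than adverse events. Section 11 provides a sponsor and statistician teleconference before each new cohort opens. Phase II has an AESI stopping rule. These limit the harm, but none sets a carfilzomib threshold, and the replacement note is optional and case by case.

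**The objective is the MTD of ruxolitinib.** Section 1.1.1 words it that way, in combination with the other two drugs, and a limit on the escalated drug is a reasonable start. The objective still presupposes that the combination was given, and Section 4.2.1.2 defines the MTD for the combination.

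**The shortfall could be stated larger.** Dividing by 336 mg/m² for every subject would give 40/336 = 12% and 152/336 = 45% for those with the lower start. That treats the protocol's own starting dose as missed exposure; their planned 264 mg/m² is the right denominator.

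**Conclusion.** The gap is real and of moderate weight. Followed as written, Section 4.3 can count a subject with 2 of 6 carfilzomib infusions (33% of plan, or 15% after the 20 mg/m² start) as a no-DLT result for an MTD defined on three drugs, and no other section prevents it. One such subject is a third of a cohort of three or a sixth of a cohort of six, and the bias is toward escalation.

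A reader might infer that the Phase I dose will be too high or that the MTD cannot be trusted. The documents do not support that. Nothing shows that such a subject will occur or how often, and the escalation probabilities above rest on assumed DLT rates and on one under-exposed subject among the first three. The defect lies in the counting rule and can be repaired without changing the design.

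**What to change.** 1. **Section 4.3.** For subjects without a DLT, add a minimum number of planned Cycle 1 carfilzomib infusions, for example 5 of 6, with the sponsor to set the threshold. State it as a count. A percentage of dose behaves differently: a subject with the 20 mg/m² start who misses one 56 mg/m² infusion has 208/264 = 79%, which fails an 80% dose rule but meets 5 of 6.
2. **Shortfalls.** Replace subjects who fall short for reasons unrelated to treatment toxicity. State in advance how a shortfall caused by treatment-related toxicity is counted, so that it does not enter the 3+3 as a no-DLT result.
3. **Reporting.** Sections 13.2.10 and 13.4.3 plan dose intensity for ruxolitinib only. Add Cycle 1 carfilzomib and dexamethasone dose intensity by cohort. For dexamethasone, an 80% limit on three doses would require all three (2/3 = 67%), so reporting is the proportionate step.
4. **Reconcile** Sections 5.1.3 and 6.3 on the infection hold, and Sections 5.3.1 and 6.3 on ruxolitinib in suspected PML. Which text is clinically right is for the sponsor to decide.

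The cost is a short addition to Section 4.3, some descriptive reporting, and an occasional replacement subject with the delay that brings. Section 9.4 already requires study treatment administration to be entered in the eCRF, so no new data are needed.
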